## **B. Study hypothesis/aims**

We propose a 48-week cohort study (N=173) to test the overarching hypothesis that symptom clusters and their associated inflammatory and metabolic pathways predict corticosteroid treatment responsiveness (primary objective outcome) and quality of life (patient-reported secondary outcome) in children 6 up to 21 years with exacerbation-prone asthma.

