## E. Study population

We will enroll a cohort of 173 children age 6 up to 21 years with exacerbation-prone asthma. Participants will be given the option to either: 1) complete a single study visit, with telephone/email contacts and a review of their electronic medical record for up to 48 weeks after enrollment, or 2) complete the 48-week cohort study with scheduled study visits. Participants who select option 2 with follow-up over 48 weeks will also have the option to complete visits 3, 4 and 5 by telephone.

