## I. Overview of study design

We will enroll a cohort of 173 children age 6 up to 21 years with exacerbation-prone asthma. Participants will be given the option to either: 1) complete a single study visit, with telephone/email contacts and a review of their electronic medical record for up to 48 weeks after enrollment, or 2) complete the 48-week cohort study with scheduled study visits (**Appendix 1**). Participants who select option 2 with follow-up over 48 weeks will also have the option to complete visits 3, 4 and 5 by telephone.

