### **Option 2: A 48-week cohort study with scheduled study visits**

Visit 1 (enrollment) will involve informed consent and participant characterization for the purpose of symptom cluster identification and receipt of systemic triamcinolone acetonide. Visit 2 will involve assessment of triamcinolone responsiveness. Visits 3, 4 and 5 are follow-up visits to assess the temporal stability of the symptom clusters. Visits 3, 4 and 5 can be completed in person or over the telephone.

This research is considered a clinical trial, because it involves an intervention (triamcinolone injection), and the study is designed to evaluate the efficacy of the intervention on symptoms and quality of life. The Emory Office of Clinical Research will facilitate the registration, periodic updates, and results reporting within ClinicalTrials.gov for the duration of the study.

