## J. Outcome measures

Asthma exacerbations are an outcome of interest for all participants.

For participants enrolled in the 48-week cohort study, the primary outcome is corticosteroid treatment responsiveness, assessed 14 days after systemic triamcinolone administration (at visit 2). Responsiveness will be determined from the mean difference in the Asthma Control Questionnaire (**ACQ**) score between visit 1 (baseline) and visit 2 (14 days), with a reduction of 0.5 considered a minimally important difference.

The secondary outcome for participants enrolled in the 48-week cohort study is quality of life, assessed by the PROMIS Pediatric Asthma Impact Scale (**PAIS**) at visits 3, 4 and 5. As with all PROMIS measures, the PAIS is scored on the T-score metric, with higher scores reflecting more of the concept being measured. On the T-score metric, 50 is the mean of the reference population and 10 is the standard deviation; thus scores of 40 and 60 are one standard deviation lower and higher than the mean of the reference population, respectively.

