## **T. Sample size**

The sample size is 173 participants age 6 up to 21 years, which accounts for a conservative attrition rate of 15% (final N=147). The following assumptions were used for sample size calculations:

- Identification of 4 symptom clusters resulting in 3 degrees of freedom,

- >80% desired power for a chi-square test of multiple proportions,
- Two-tailed significance level of 0.05 if the effect size (W) is small-to-medium by Cohen's convention and equivalent to W=0.275 (small effect: W=0.10, corresponding odds ratio=1.49; medium effect: W=0.30, corresponding odds ratio=3.45), and
- Sample size allocation ratio of 1-2 per cluster group and sample sizes of at least 20 per group.

The sample size calculations with the above parameters should achieve at least 80% power as shown in **Table 3**.

For the secondary outcome, The sample size of 173 children necessary for the primary outcome should achieve >85% power to detect a difference of 0.2 between group means (considered a small effect size  $d$ ) with standard deviation of 0.20. Power >80% is achieved if the mean difference between groups and associated standard deviation is slightly larger but still small (0.25-0.30). In our prior study of triamcinolone administration to children with asthma, mean ( $\pm$  standard deviation) quality of life scores (on a different instrument, the Asthma Quality of Life Questionnaire) were 6.17 ( $\pm$  0.75) and 5.07 ( $\pm$  0.99), respectively. If similar differences are noted between two symptom cluster groups, we should have >90% power for the primary outcome and >95% for the secondary outcome if the groups have at least 20 participants. With smaller group sizes of only 13 participants, power would be >81% and >89% for the primary and secondary outcomes, respectively.

Drop-out	df	Power if effect size is:				
		0.250	0.275	0.300	0.325	0.350
10% (N=156)	3	0.749	0.833	0.897	0.941	0.969
	4	0.703	0.795	0.867	0.920	0.956
	5	0.664	0.760	0.840	0.900	0.942
12.5% (N=151)	3	0.734	0.820	0.886	0.933	0.963
	4	0.687	0.780	0.855	0.911	0.949
	5	0.648	0.744	0.826	0.889	0.934
15% (N=147)	3	0.721	0.808	0.877	0.926	0.959
	4	0.674	0.767	0.844	0.903	0.943
	5	0.634	0.731	0.814	0.878	0.927

**Table 3.** Estimated power.

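### Section T powers the primary outcome on all 173 enrolees less 15% attrition, although only children who choose Option 2 can have that outcome

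*Combined protocol and SAP*

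**What the plan says.** Section T states: "The sample size is 173 participants age 6 up to 21 years, which accounts for a conservative attrition rate of 15% (final N=147"). Its power paragraph and Table 3 use that N for a chi-square test across four symptom clusters, and its secondary-outcome paragraph again speaks of "The sample size of 173 children necessary for the primary outcome". The two participation options are not mentioned anywhere in Section T.

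Section I says "We will enroll a cohort of 173 children age 6 up to 21 years with exacerbation-prone asthma", and Sections E and I both continue: "Participants will be given the option to either: 1) complete a single study visit" with remote follow-up, or 2) the 48-week cohort with scheduled visits. No expected split, cap or Option 2 minimum is given.

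Section J opens its outcome definition with participants in the 48-week cohort, for whom "the primary outcome is corticosteroid treatment responsiveness, assessed 14 days after systemic triamcinolone administration (at visit 2"). It restricts the next outcome in the same way: "The secondary outcome for participants enrolled in the 48-week cohort study is quality of life". Under Option 2 in Section I, "Visit 2 will involve assessment of triamcinolone responsiveness". In Section K, the Option 1 schedule has no triamcinolone and no week 2 assessment; after baseline, its ACQ contacts are at weeks 24 and 48.

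Section B describes the study differently: "We propose a 48-week cohort study (N=173").

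**The concern.** The primary test in Section U compares, across latent classes, the proportion of children whose ACQ improves by at least 0.5 from visit 1 to visit 2. An Option 1 child has no visit 2 ACQ and was never given the drug whose effect is being measured, so that child contributes nothing to the test. If 173 counts both options, as Sections E and I say, the N available is 173 less the Option 1 children, less losses before visit 2. Section T removes only the losses.

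The 15% cannot be read as covering Option 1. The text calls it attrition and Table 3 calls it drop-out, whereas choosing Option 1 is a permitted enrolment choice.

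At stake is the study's main power statement. If the primary comparison is null, a reader will judge it against 0.808, and that figure describes the test only if 147 Option 2 children have both ACQ scores.

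**Working it through.** **Inputs.** From Section T: total 173; attrition 15%; 4 clusters, so df = 3; alpha 0.05; W = 0.275; target power above 80%. The documents give neither the share choosing Option 2 nor the loss by visit 2. Both are assumptions below, apart from the plan's 15%, which is not tied to any visit.

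**Formula.** Power = 1 − F(c; df, λ), where F is the noncentral chi-square distribution function, c is the 95th percentile of the central chi-square with the same df, and λ = N × W².

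**Reproducing the plan.** 173 × 0.85 = 147.05, so N = 147. With W² = 0.275² = 0.075625, λ = 147 × 0.075625 = 11.117 and power = 0.808, as in Table 3. All 45 cells of Table 3 reproduce to within 0.001. The arithmetic is sound; the question is which children the 147 are.

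**Evaluable N for 80% power.** N = 145 gives 0.8025 and N = 144 gives 0.7995, so 145 are needed. The plan's margin is 147 − 145 = 2 children.

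**Option 2 enrolees needed**, 145/(1 − loss), rounded up:

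| Loss to visit 2 | Option 2 enrolees | Share of 173 | Room for Option 1 |
|---|---|---|---|
| 0% | 145 | 84% | 28 |
| 5% | 153 | 88% | 20 |
| 10% | 162 | 94% | 11 |
| 15% | 171 | 99% | 2 |

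**Power at W = 0.275 by assumed Option 2 share**, with N = 173 × share × (1 − loss), rounded down. Cells show N and power:

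| Loss | 90% share | 80% share | 70% share | 50% share |
|---|---|---|---|---|
| 0% | 155, 0.831 | 138, 0.781 | 121, 0.719 | 86, 0.555 |
| 5% | 147, 0.808 | 131, 0.757 | 115, 0.695 | 82, 0.533 |
| 10% | 140, 0.787 | 124, 0.731 | 108, 0.664 | 77, 0.505 |
| 15% | 132, 0.760 | 117, 0.703 | 102, 0.636 | 73, 0.482 |

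**Detectable W.** At 15% loss, the W giving 80% power is about 0.273 if all 173 choose Option 2, 0.306 at an 80% share and 0.387 at a 50% share.

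**Sensitivity to effect size.** At W = 0.325, 104 evaluable children give 80% power, and N = 117 gives 0.852.

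**The case against.** The strongest reply is that 173 was meant as the Option 2 number. Section B calls the study a 48-week cohort of 173, and Section J uses the same term for Option 2. On that reading Table 3 stands, and what remains is a conflict over what 173 counts. This is possible, but Sections E and I say plainly that the 173 may choose either option, so one set of statements has to change.

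A second reply is that the size of the loss is assumed. This is right. The plan offers no support for a 50% share, and the 15% rows are pessimistic for an outcome measured at two weeks if the 15% was meant for the full 48 weeks. At 0 to 5% loss, an Option 2 share of about 84 to 88% still gives 80% power. The omission does not depend on the split, but its consequence does.

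A third reply concerns the secondary outcome, and it largely stands. Section T's claim of more than 85% power is for a difference of 0.2 with SD 0.20, a standardized difference of 1.0. Two groups of 20 already give 0.869, so that claim does not need all 173. Option 1 children also complete an asthma impact questionnaire at weeks 24 and 48. No secondary power loss is shown; only the number attached to that sentence is wrong if 173 is total enrolment.

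Finally, Section J does name the primary-outcome population, so Section U's silence is untidy but leaves no real doubt about who can be analysed.

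**Conclusion.** The concern holds. As written, Section T credits the primary test with children who cannot have the primary outcome. Its 0.808 is reached only if 147 Option 2 children have ACQ at visits 1 and 2, and 80% power requires 145. At the plan's own 15% loss, no more than 2 of the 173 may choose Option 1; with no loss at all, no more than 28 (16%).

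Whether power is actually short cannot be told from the documents. A 90% Option 2 share with 5% loss or less keeps the planned power. An 80% share gives 0.70 to 0.78 across losses of 15% to 0%. These figures assume W = 0.275, four classes and the stated shares; a larger true effect would remove much of the shortfall. The point should be corrected, but it does not show that the trial is underpowered.

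**What to change.** In Section T, name the primary-outcome population: injected Option 2 participants with ACQ at visits 1 and 2. Repeat this in one sentence in Section U. Restate Table 3, as power or as detectable W, for the Option 2 number expected to be evaluable at visit 2, using a loss rate specific to that visit. In the secondary-outcome sentence, replace 173 with the Option 2 number followed through visits 3 to 5. Make Sections B, E, I and T agree on whether 173 is total or Option 2 enrolment.

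This costs only text: one paragraph and table in Section T, a sentence in Section U and small edits elsewhere. No procedure changes.

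The alternative is an Option 2 enrolment target of 145/(1 − loss), for example 153 at 5% or 171 at 15%. That is not cheap. Within a total of 173 it nearly removes the choice between options. Otherwise total enrolment must rise: at an assumed 80% share and 15% loss, 145/(0.85 × 0.80) = 213.2, so 214 children.

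Two clerical points can be settled in the same edit. The dosing sentence in Section L should be limited to Option 2 participants, and Section H should make clear whether all Option 2 participants or only some of them are injected.

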The secondary outcome, quality of life, will be compared with generalized estimating equations at visits 3, 4 and 5 using latent class assignment as the predictor. Analyses will be evaluated in light of pertinent covariates such as age, sex, race, ethnicity, socioeconomic status, medications, exposures and allergic sensitization. A 0.05 significance threshold will be utilized for secondary analyses without adjustment for multiple comparisons.

Metabolomic data, cytokine data, and amino acid data will be quantitative, linear mixed effects models will be used to determine the association between these symptom cluster group assignment.

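### The secondary-outcome power statement labels a one-SD difference (0.2 with SD 0.20, d = 1.0) as a small effect; at d = 0.2 single-visit power is roughly 10-26%

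*Combined protocol and SAP*

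**What the plan says.** Section T (Sample size) makes two statements about power for the secondary outcome.

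- The sample of 173 "should achieve >85% power to detect a difference of 0.2 between group means (considered a small effect size" d), "with standard deviation of 0.20".
- Power stays above 80% if the difference and its SD are "slightly larger but still small (0.25-0.30").

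The assumptions listed earlier in section T, for the primary outcome, are four clusters, 147 evaluable children, and "Sample size allocation ratio of 1-2 per cluster group and sample sizes of at least 20 per group". Section T names no test, class sizes or within-child correlation for the secondary-outcome figure.

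Section J (Outcome measures) defines the endpoint: "The secondary outcome for participants enrolled in the 48-week cohort study is quality of life", measured by the PROMIS Pediatric Asthma Impact Scale as a T-score on which "50 is the mean of the reference population and 10 is the standard deviation". Section U, in the plan for aims 1-3, says that quality of life "will be compared with generalized estimating equations at visits 3, 4 and 5 using latent class assignment as the predictor", at a 0.05 threshold without multiplicity adjustment.

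**The concern.** Cohen's d is the mean difference divided by the SD. The power statement calls 0.2 a small d, yet supplies an SD that makes the standardised difference 1.0. It appears that the raw difference was taken for d. The second statement has the same problem, because differences and SDs that both lie between 0.25 and 0.30 give effects of about one SD.

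The inputs are also not on the scale of the endpoint. An SD of 0.20 cannot describe a T-score whose reference SD is 10, so section T does not tell the reader what difference in T-score points the study can detect.

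Quality of life is the named patient-reported secondary outcome and half of the Aim 2 hypothesis. A reader who accepts the statement would believe that the study can detect small quality-of-life differences between clusters, and could take a null result as evidence against them.

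**Working it through.** **Inputs.** From section T: difference 0.2, SD 0.20, the range 0.25-0.30, at least 20 per group, allocation ratio 1-2, four clusters, 173 enrolled and 147 evaluable. Significance is two-sided 0.05 (two-tailed in section T; the 0.05 threshold for secondary analyses is in section U). Reference SD 10 is from section J. Assumed here, because the documents do not give them: actual class sizes, a two-class comparison, and the within-child correlation ρ.

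**Method.** For two classes of n1 and n2, the noncentrality is d × √(n1·n2/(n1+n2)), with n1+n2−2 degrees of freedom. Power comes from the noncentral t distribution.

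**Step 1: reproduce the plan's figure.** d = 0.2/0.20 = 1.0. With 20 v 20 the noncentrality is 1.0 × √(400/40) = 3.16, and power is 0.869 (0.885 by normal approximation). This agrees with the stated >85%.

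**Step 2: the second statement.** Possible ratios are 0.25/0.30 = 0.83, 0.25/0.25 = 0.30/0.30 = 1.0, and 0.30/0.25 = 1.2. None is small. At 0.25/0.30 with 20 per class, power is 0.728, so the >80% claim also fails for that pairing at that class size.

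**Step 3: power at d = 0.2.** For the mean of three visits, d is multiplied by √(3/(1+2ρ)). That gives 0.2 × 1.225 = 0.245 at ρ = 0.5 and 0.2 × 1.732 = 0.346 at ρ = 0.

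| Classes compared | One visit | Three visits, ρ = 0.5 | Three visits, ρ = 0 |
|---|---|---|---|
| 20 v 20 (stated minimum) | 0.095 | 0.117 | 0.187 |
| 20 v 40 (1:2 allocation) | 0.111 | – | – |
| 37 v 37 (147/4 ≈ 37) | 0.136 | 0.180 | 0.312 |
| 73 v 74 (147 in two classes) | 0.226 | 0.314 | 0.550 |
| 86 v 87 (173 in two classes, no attrition) | 0.258 | 0.360 | 0.620 |

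An overall four-class ANOVA with 147 children and extreme class means 0.2 SD apart gives 0.10 to 0.15 at a single visit, depending on where the middle classes lie.

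**Step 4: size needed for 85% power at d = 0.2.** One visit needs 450 per class. Multiplying by (1+2ρ)/3 gives 301 per class at ρ = 0.5 and 151 per class at ρ = 0. Even the last is 2 × 151 = 302 children in two classes, against 173 enrolled.

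**Step 5: what is detectable with 85% power at one visit.** d = 0.972 (20 v 20), 0.835 (20 v 40), 0.706 (37 v 37) and 0.498 (73 v 74). Multiplied by the reference SD of 10, these are 9.7, 8.3, 7.1 and 5.0 T-score points.

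**The case against.** The strongest reply is that the origin of the >85% figure is not documented. The protocol attributes it to 173 children, not to 20 per group, and at d = 1.0 with 147 children in four equal classes power would be about 0.99. A two-group ANOVA with f = 0.25 and 147 children also gives 0.853. This stands as a caution about how the figure was produced: the match at 20 per group is a plausible reconstruction, not a confirmed one. It does not rescue the label, because the ANOVA match corresponds to d = 0.5 and no between-group calculation tried reached 85% at d = 0.2.

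A second reply is that the upper end of the 10-26% range departs from the plan, since it needs two classes and no attrition. That is correct. With four equal classes and 147 children the figure is about 13-14%, which is the fairer planning value.

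A third reply is that section T also gives a benchmark from the prior triamcinolone study: 6.17 (SD 0.75) against 5.07 (SD 0.99). The pooled SD is √((0.75² + 0.99²)/2) = 0.878, so d = 1.10/0.878 = 1.25. Power with 20 per group is 0.97, consistent with the stated >95%. This shows adequate power for a large effect on what the protocol itself says is a different instrument. It leaves the claim about a small effect uncorrected.

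Finally, the outcome is secondary and the statement does not drive the sample size. That limits the consequence but does not make the statement true.

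**Conclusion.** The concern holds. The stated scenario is a difference of one full SD, and the design does not have 85% power for a small effect. At d = 0.2, single-visit power is about 10% at the stated minimum class size, about 14% at 37 per class, and 26% at most. Using all three follow-up visits with an assumed correlation of 0.5 gives 12% to 36%; zero correlation with two classes and no attrition gives 62%.

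These figures rest on assumed class sizes, a two-class comparison at two-sided 0.05, and an assumed correlation. The number of Option 2 participants with follow-up is not given. Because the secondary outcome is defined only for them, class sizes based on 147 or 173 children are likely to be favourable.

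**What to change.** In section T, delete the parenthesis that calls the 0.2 difference a small d, and delete the words in the next statement that call 0.25-0.30 still small. Replace both power claims with a detectable difference in Asthma Impact T-score points, at the class sizes expected among Option 2 participants with follow-up. State the assumed SD, number of visits, within-child correlation, test and significance level. Replacing both claims also removes the >80% figure that fails at 0.25/0.30 with 20 per class.

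As an illustration with 85% power, two classes and two-sided 0.05:

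| Class sizes | One visit, SD 10 | One visit, SD 8 to 12 | Mean of three visits, ρ = 0.5, SD 10 |
|---|---|---|---|
| 20 v 20 | about 10 points | 7.8-11.7 | about 8 |
| 37 v 37 | about 7 points | 5.6-8.5 | about 6 |
| 73 v 74 | about 5 points | 4.0-6.0 | about 4 |

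SD 10 is the reference-population value, not an estimate for this cohort, so the team should substitute its own if it has one.

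The cost is a short recalculation, an explicit estimate of Option 2 follow-up numbers, and a less favourable statement of sensitivity. The design, the sample size and Table 3 do not change.

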## U. Statistical analysis plan

### Plan for parent R01 study (aims 1-3)

Latent transition analysis (**LTA**) is a cluster-based model that allows for integration of repeated data. Discrete latent classes of individuals are identified based on their shared characteristics across a set of observed categorical variables and models are allowed to change over time between classes. Parameters estimated in LTA include class membership probabilities and item response probabilities, which are used to characterize the group structures. LTA also produces a transition probability matrix, estimating probabilities of membership in the same group at each time point (entries along the diagonal) and probabilities of transitioning to a different group over time (entries off the diagonal). Parameters are combined mathematically into a likelihood function, and the set that maximizes the likelihood function determines the membership of each individual in one of the latent classes.

Because LTA is aimed at characterizing transition over time, it requires variability in all variables. Therefore, we will perform LTA with patient-reported symptoms (global, mental, social and physical health categories) and measures of asthma disease activity (ACQ, ACT, lung function, exhaled nitric oxide, blood eosinophils) measured at baseline and visits 3, 4 and 5 (**see Appendix 1**). Age, sex, race, ethnicity, socioeconomic status, medications, exposures and allergic sensitization measured at the baseline visit will be considered stable and treated as covariates in the LTA model. All participants will be included in the analysis since missing data for the variables are handled in the procedure, with data assumed to be missing completely at random. The test of the null hypothesis that data are missing completely at random (Missing Completely At Random test in the SAS LTA procedure) will be evaluated; if non-significant, missingness does not affect the interpretation of the results. The number of classes will be statistically determined using the Bayesian information criterion (**BIC**) and class prevalence if BICs are of a similar magnitude, to avoid a solution leading to low prevalent groups (<5%). To assess the stability of the group structure, goodness of fit of the “constrained” LTA model in which identical item-response probabilities across time are estimated (i.e., the same cluster structure is forced into multiple time points) will be compared with the “unconstrained” LTA model in which item response probabilities are estimated at each time point. To further address sex as a biological variable, models will also be fitted by sex, with statistical comparison of results observed in boys and girls. All analyses will be performed with SAS software version 9.4 (SAS Institute) using the PROC LTA procedure.

The primary outcome will be assessed after assignment of individuals to the latent classes that they had the highest probability of belonging to (based on the posterior probability provided by the model at baseline). A straightforward analysis of the primary outcome will follow and involves comparison of the proportion of children achieving a minimally importance difference in ACQ of at least 0.5 in each of the latent classes via a Chi-Square test.

The secondary outcome, quality of life, will be compared with generalized estimating equations at visits 3, 4 and 5 using latent class assignment as the predictor. Analyses will be evaluated in light of pertinent covariates such as age, sex, race, ethnicity, socioeconomic status, medications, exposures and allergic sensitization. A 0.05 significance threshold will be utilized for secondary analyses without adjustment for multiple comparisons.

Metabolomic data, cytokine data, and amino acid data will be quantitative, linear mixed effects models will be used to determine the association between these symptom cluster group assignment.

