## L. Procedural details

**Asthma control evaluation.** Asthma control and associated respiratory symptoms will also be assessed with the Asthma Control Questionnaire (**ACQ**) and the Asthma Control Test (**ACT**). The ACQ can be completed by children down to 6 years with strong measurement properties when administered by a trained interviewer. The ACQ is sensitive to short-term changes in asthma control and has well-documented reliability and cross-sectional and longitudinal validity in diverse asthma populations across a wide range of severities. This 7-item questionnaire includes questions related to daytime and nocturnal symptoms, short-acting bronchodilator use, and lung function during the clinic visit on that day. A higher score indicates poorer asthma control. The ACT can be completed directly by children 12 years and older; children 6-11 years will complete the Childhood ACT (**C-ACT**). Both tools have been extensively validated and have excellent measurement properties. For both tests, individual items about respiratory symptoms (5 and 7 in total for ACT and C-ACT, respectively) are summed; scores of 19 or less reflect uncontrolled asthma.

**PROMIS symptom questionnaires.** Symptoms will be assessed with validated PROMIS measures for children. PROMIS measures will be completed directly by children age 8-21 years, with caregiver assistance for children 6-7 years. The following PROMIS short-form measures will be utilized:

- Pediatric Life Satisfaction (4a)
- Pediatric Meaning and Purpose (4a)
- Pediatric Physical Stress Experience (4a)
- Pediatric Physical Activity (4a)
- Pediatric Positive Affect (4a)
- Pediatric Psychological Stress Experiences (4a)
- Pediatric Family Relationships (4a)
- Pediatric Asthma Impact (8a)
- Pediatric Anger (5a)
- Pediatric Anxiety (8a)
- Pediatric Depressive Symptoms (8a)
- Pediatric Fatigue (10a)
- Pediatric Peer Relationships (8a)

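### As written, the plan lets Asthma Impact, the secondary outcome, serve as an indicator of the latent classes that are used to predict it

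*Combined protocol and SAP*

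**What the plan says.** - **Class formation (section U, aims 1-3).** The latent transition analysis is described thus: "we will perform LTA with patient-reported symptoms (global, mental, social and physical health categories) and measures of asthma disease activity". The named disease-activity measures are ACQ, ACT, lung function, exhaled nitric oxide and blood eosinophils, all "measured at baseline and visits 3, 4 and 5". The four symptom categories are not mapped to instruments.
- **Symptom instruments (section L).** Symptoms are assessed with PROMIS measures. Thirteen short forms are listed under the PROMIS symptom questionnaires, and the eight-item Asthma Impact form is among them.
- **Collection (section K, Option 2, and Appendix I).** At visits 3, 4 and 5 Asthma Impact is collected only through that battery. Appendix I has a single PROMIS row.
- **Secondary outcome (section J).** "The secondary outcome for participants enrolled in the 48-week cohort study is quality of life, assessed by the PROMIS Pediatric Asthma Impact Scale", at visits 3, 4 and 5.
- **Secondary analysis (section U).** The outcome, "quality of life, will be compared with generalized estimating equations at visits 3, 4 and 5 using latent class assignment as the predictor".
- **Class assignment (section U).** The only rule given is written for the primary outcome: each child goes to the most probable class, "based on the posterior probability provided by the model at baseline".
- **Number of classes (section U).** "The number of classes will be statistically determined using the Bayesian information criterion", with class prevalence used when BIC values are similar.

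**The concern.** Section B and Aim 2 present quality of life as something that symptom clusters predict. If Asthma Impact is itself an indicator, part of any association is the scale predicting itself. There are two routes. The scale's baseline value helps place a child in a class, and it is correlated with the same child's later values. Its values at visits 3-5, which are the outcome data, also enter the fit directly.

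The result would overstate how well the other symptoms predict quality of life. The threshold gives no protection: "A 0.05 significance threshold will be utilized for secondary analyses without adjustment for multiple comparisons".

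**Working it through.** **1. The plan's own figures.** No stated figure is in dispute. 173 × 0.85 = 147.05, the final N of 147 in section T. Power in Table 3 for N = 147, W = 0.275 and 3 df uses noncentrality 147 × 0.275² = 11.12 and gives 0.808, as printed. All 45 cells reproduce within 0.001.

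**2. The texts side by side.** Section L: symptoms are measured by 13 PROMIS forms, including Asthma Impact. Section U: patient-reported symptoms enter the LTA at baseline and visits 3-5. Section J: Asthma Impact at visits 3-5 is the outcome. Section U again: that outcome is regressed on class. No section takes Asthma Impact out of the indicators.

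**3. Why the baseline class does not fully separate them.** In a jointly fitted LTA the baseline posterior is

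P(C₁ = k | Y₁, Y₃, Y₄, Y₅) ∝ π_k · P(Y₁ | k) · P(Y₃, Y₄, Y₅ | C₁ = k).

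The last factor uses visit 3-5 data. With Asthma Impact among the indicators, that factor contains the outcome.

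**4. Size.** Three separately coded simulations used the null that isolates this defect: Asthma Impact unrelated to any class. The documents give none of the following inputs except N = 147 and the BIC rule:
- four true classes with 80% persistence between occasions (settings stated for A);
- binary items, with Asthma Impact split at its median when included;
- within-child correlation of Asthma Impact 0.5;
- number of classes chosen by BIC from 1-4 (A also fitted 5 when 4 was best);
- test: analysis of variance of each child's mean visit 3-5 score on baseline class, standing in for the GEE test (A and C);
- complete data and no covariates.

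A used 14 other indicators. C used 14, and also 17: the other 12 PROMIS forms plus the five disease-activity measures (12 + 5 = 17). The count for B is not recorded. Item probability is the assumed class separation, from 0.85 (strong) to 0.65 (weak).

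Rejection at nominal 5%, Asthma Impact in / left out:

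| Item probability | A (14) | B | C (14) | C (17) |
|---|---|---|---|---|
| 0.85 | 3.5 / 3.0 | – | – | – |
| 0.75 | 7.2 / 5.5 | 5.8 / 4.8 | 6.7 / 5.0 | 6.7 / 4.7 |
| 0.70 | 8.5 / 4.5 | 8.8 / 5.3 | – | 8.8 / 5.0 |
| 0.65 | 18 / 7.5 | 22 / 6.5 | 18.5 / 5.0 | 14.5 / 5.7 |

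The excess (in minus out) is 1.0-2.0 points at 0.75, 3.5-4.0 at 0.70 and 8.8-15.5 at 0.65.

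A used 400 runs at 0.75 and 0.65, and 200 at 0.85 and 0.70. B used 400 throughout. C (14) used 1,100 at 0.75 and 2,180 at 0.65. With 400 runs the standard error is √(0.05 × 0.95 / 400) = 1.1 points near 5% and √(0.18 × 0.82 / 400) = 1.9 near 18%. Left out, class and outcome are independent by construction, so the 7.5% is simulation noise; 2,180 runs gave 5.0%.

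In A, BIC chose four classes in every LTA run at 0.75 and 0.85, three in 88-99% at 0.70, and two in 74-92% at 0.65.

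**5. A second null that does not isolate the defect.** Simulation A was also run with the baseline class unrelated to later classes, while Asthma Impact followed the concurrent class. In / left out: 4.5/3.5 at 0.85, 10/11 at 0.75, 13/6 at 0.70 and 14/12.5 at 0.65. Leaving Asthma Impact out brings no consistent reduction, so these figures are not counted. They reflect the overlap in step 3, which remains for the other indicators, and they matter only if the stability hypothesis of Aim 1 fails.

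**The case against.** **Exclusion may be intended.** Section B, Aim 2 and section J treat quality of life as an outcome distinct from symptoms. Section K groups Asthma Impact with asthma control at the 24- and 48-week contacts, and section U does not name it among the disease-activity measures. This stands as evidence of intent. But the section K grouping covers Option 1 contacts only, and a programmer following sections L and U would include the scale. A reader might infer that the plan definitely puts the outcome into its predictor; the documents show only that their wording permits it.

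**The class occasion.** A reader might infer that the GEE predictor is undefined. That goes too far. The baseline posterior is the only assignment rule given, and section I ties visit 1 to cluster identification and visits 3-5 to temporal stability. The rule should be repeated for the secondary outcome, but this is a note on wording.

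**The effect is small where the four clusters assumed in section T are recovered.** This stands: 1-2 points at 0.75 and no detectable excess at 0.85. The large figures arise where BIC mostly keeps two classes.

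**Larger figures are possible.** With the number of classes forced to four, the baseline-class test rejected in 53% of runs with 12 other indicators and 21.5% with 17. These do not describe this plan, which selects the number of classes by BIC.

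**Conclusion.** The point holds as a gap in the text with a conditional effect. Nothing keeps Asthma Impact out of the LTA, and if it goes in, the secondary test is biased towards finding an association.

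With Asthma Impact unrelated to any class, rejection at nominal 5% (in against left out) was about 3.5% against 3% at item probability 0.85, 6-7% against 5% at 0.75, 8.5-9% against 4.5-5% at 0.70, and 14.5-22% against 5-7.5% at 0.65. The 14.5% is with 17 other indicators. All of this rests on the assumed settings. The documents give no expected class separation, so they do not show where in this range the study will fall.

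The change should be made before the secondary analysis is run. It does not call the sample size or the primary endpoint definition into question.

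**What to change.** 1. In section U, state that Asthma Impact is not an indicator in the LTA. Use one set of classes for all aims, and list which of the other 12 PROMIS measures form each of the four symptom categories.
2. As a wording note in the secondary-outcome paragraph, state that the GEE predictor is the baseline class already defined for the primary outcome. Label any analysis by visit-specific class as concurrent association.
3. Optionally, add a sensitivity analysis with classes from visit 1 data only, fixing their number at the LTA's choice. Left to BIC at item probability 0.65, visit 1 data alone gave a single class in 395-399 of 400 runs.

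**Cost.** SAP wording and, for item 3, one extra model fit on data already collected. One of 13 PROMIS measures leaves the LTA. Because the primary chi-square test uses the same classes, class membership there, and possibly the number of classes, may change. The primary endpoint definition, sample size and Table 3 do not.

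Some power may be lost when separation is weak. In simulation A with a real modest association, the LTA without Asthma Impact had 63% power, equal to the true classes, at 0.75. At 0.65 it had 43% against 64%, with BIC mostly keeping two classes; the runs do not show how much of that gap is due to the one omitted measure. Visit-1-only classes had less power still (41% at 0.75 and 17% at 0.65), so they suit a sensitivity analysis and not a replacement.
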